3. Bipolar Disorder medications (if used to treat Bipolar Disorder or manic symptoms. Other uses may be eligible pending Study Physician approval).

Medical Exclusion Criteria

1. Women who are pregnant, planning a pregnancy within the next 12 months, or lactating.
2. History of epilepsy or seizure disorder (history of seizure requires Study Physician approval).
3. History of kidney disease, including transplant.
4. Uncontrolled hypertension (SBP >160 or DBP >100).
 - a. Note: If a participant presents with blood pressure greater than 160/100 at sessions occurring on Week 0 (Pre-Quit) or at any other point during the treatment period, they will not be provided with/able to continue on medication unless the Study Physician grants approval.
5. History of unstable heart disease, stroke or myocardial infarction, angina, abnormal heart rhythms, or tachycardia (as determined by Study Physician review or self-report).
6. Any suicide risk score on MINI, current suicidal ideation on Columbia scale, or lifetime self-reported suicide attempt.
7. Current or past diagnosis of psychotic or bipolar disorder, as determined by self-report or MINI assessment.
8. Current diagnosis of unstable and untreated major depression, as determined by self-report or MINI assessment (eligible if stable for ≥ 30 days).
9. Previous allergic reaction to varenicline.

General Exclusion Criteria

1. Any medical condition or concomitant medication that could compromise subject safety or treatment, as determined by the Principal Investigator and/or Study Physician.
2. Inability to provide informed consent or complete any of the study tasks as determined by the Principal Investigator and/or Study Physician.

5. Vulnerable Populations

Children, pregnant women, fetuses, neonates, or prisoners are not included in this research study.

6. Populations vulnerable to undue influence or coercion

Educationally or economically disadvantaged persons are included but not solely targeted for recruitment. Cognitively impaired persons are not included in the current study. Because of our recruitment efforts for this study, it is possible that University of Pennsylvania employees and students may be invited to participate. Status of participation in the study will be independent of the subject's work or school activities.

7. Subject Recruitment

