At the completion of the study, there will be a final reconciliation of drug shipped, drug consumed, and drug remaining. This reconciliation will be logged on the drug reconciliation form, signed and dated by the research staff. Any discrepancies noted will be investigated, resolved, and documented prior to return or destruction of unused study drug. Drug destroyed on site will be documented in the study files.

STUDY PROCEDURES

1. Procedures

Subjects

Subjects will be 374 adult smokers who have been diagnosed with cancer in the last 5 years, meet study eligibility criteria, and provide written consent to participate in this between-subject trial.

Study Procedures

Initial Eligibility Screening.

Recruited subjects will complete an initial eligibility assessment in the oncology clinic or over the telephone. This assessment reduces the likelihood that participants attend an Intake Session only to learn that they are ineligible or to allow us to ascertain physician's clearance should the participants have a medical condition that requires approval. Subjects who pass this pre-screening will be invited to attend an Intake Session.

Intake Session (Week -1): Consent, Eligibility Determination, Baseline Measures.

Subjects who pass the pre-screening will be invited to attend a 2.5-hour Intake Session where the following activities will occur:

1. Subjects will hear a study description where all study procedures, risks, and information about the study medication will be reviewed. Subject questions will be answered. Following this presentation, the combined informed consent and HIPAA form will be completed.
2. A urine pregnancy test (all female subjects) will be administered.
3. A breath alcohol concentration assessment (BrAC) to control for alcohol consumption. The handheld device uses a disposable mouthpiece, reports the concentration of alcohol in breath and takes about 2 minutes.
4. A carbon monoxide (CO) breath assessment to control for prior tobacco exposure. The handheld device uses a disposable mouthpiece, reports CO in parts per million (ppm), and takes about 3 minutes.
5. A mental status examination (Mini International Neuropsychiatric Interview, HADS, CSSRS) with a trained research staff member.
6. Complete routine medical history, including blood pressure assessment. If a participant has not received a Karnofsky or ECOG score within 6 months of enrollment the Karnofsky scale will also be administered.
7. A concomitant medication review.

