8. Complete baseline paper and pencil measures to assess 1) background variables that may serve as covariates and will allow for assessment of external validity (e.g., smoking history, demographics); 2) mediators (e.g., affect), 3) moderators (e.g., disease-related information), and 4) baseline smoking behavior.

If eligible at this point, subjects will be scheduled for the first treatment session (Week 0). There must be no more than 60 days between the Intake Session and the first treatment session (Week 0, Pre-Quit). If 60 days elapses between these sessions, all intake measures must be re-administered and evaluated by the study physician before Pre-Quit can occur (both sessions may be completed on the same day pending study physician approval by phone).

Behavioral Counseling (Week 0-Week 18).

All subjects will receive manual-based counseling from a counselor trained and supervised by [name]. The counseling protocol is based on PHS guidelines for smoking cessation treatment (Fiore et al., 2008), used in our past studies with cancer patients ([name] et al., 2010a) and in our ongoing cessation trial at NU (R01 DA025078). Counseling is included given its efficacy at helping smokers quit (Fiore et al., 2008) and to increase study retention. Counseling is provided to both treatment arms through Week 18 to equate for time and attention across arms and since this method was used in varenicline clinical trials (Gonzales et al., 2006) and in our extended therapy trial ([name] et al., 2010b). In-person counseling was selected for most sessions to ensure adequate monitoring of participant safety and adherence throughout the trial. Sessions are arranged at convenient times for the participants, including evenings.

Pre-Quit Session (Week 0): The counseling program begins at Week 0 with a 1-hour in-person "pre-quit" counseling session to prepare for the target quit day. This session focuses on reviewing participant's history and experience with quitting, beliefs about smoking and quitting, and perceived barriers to cessation, and

initiates a quitting plan involving identifying smoking triggers and identifying strategies to increase the chance for success, including relying on social support and altering behaviors associated with smoking. Medication is dispensed at this session and will begin following the session.

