Note: If a participant is unable to complete a session in-person, assessments and counseling may be completed over the telephone. Every attempt will be made to accommodate participants' schedules & reduce the likelihood of missed sessions. Missed sessions will not be submitted as protocol deviations.

Table 2: Study Measures/Events

| Study Week | -1 | 0 | 1 | 4 | 8 | 12 | 14 | 18 | 24 | 26 | 52 |
|--|-----------|----------------|----------------|----------------|----------------|----------------|----------------|----------------|----------------|----------------|----------------|
| Session Name | Intake | Pre-Quit | TQD | W4 | W8 | W12 | W14 | W18 | W24 | W26 | W52 |
| Session Type | In Person | In Person | In Person | In Person | Phone | In Person | Phone | Phone | In Person | Phone | In Person |
| TREATMENT | | | | | | | | | | | |
| Standard Varenicline | | X | X | X | X | X | | | | | |
| Extended Varenicline | | X | X | X | X | X | X | X | X | | |
| Counseling | | X | X | X | X | X | X | X | | | |
| SCREENING/COVARIATES | | | | | | | | | | | |
| Urine Pregnancy Screen | X | | | | | | | | | | |
| Breath Alcohol Concentration | X | | | | | | | | | | |
| Blood Pressure | X | X | X | X | | X | | | X | | X |
| Psychiatric History (MINI) | X | X ^a |
| Medical History | X | | | | | | | | | | |
| Concomitant Medications | X | X | X | X | X | X | X | X | X | X | X |
| Demographics | X | | | | | | | | | | |
| Smoking History/FTND | X | | | | | | | | | | |
| ETOH History | X | | | | | | | | | | |
| Depression/Anxiety (HADS) | X | X | X | X | X | X | X | X | X | X | X |
| Lifetime MDE ([name] et al., 2011) | X | | | | | | | | | | |
| MEDIATORS | | | | | | | | | | | |
| Withdrawal Symptoms (SJWF) | | X | X | X | | X | X | | X | X | |
| Smoking Urges (QSU-B) | | X | X | X | | X | X | | X | X | |
| Affect (PANAS) | | X | X | X | | X | X | | X | X | |
| Cognitive Function (FACT-2) | | X | X | X | | X | X | | X | X | |
| Cigarette Evaluation Scale (CES) ^c | | X | X | X | X | X | X | X | X | | |
| Cue-elicited smoking urges (Choice Performance Task) | | X | X | X | | X | | | X | | X |
| Pearlin Mastery Scale (PMS) | X | | X | X | | | | | | | |
| TREATMENT VARIABLES | | | | | | | | | | | |
| Adherence (Pill Count) | | | X | X | X | X | X | X | X | X | |
| Adherence (Blood) | | | | X ^b | | | | | | | |
| Side Effects Checklist (SEC) | | X | X | X | X | X | X | X | X | X | X |
| Side Effects (Open-Ended) | | | X | X | X | X | X | X | X | X | X |

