| Suicidality (CSSRS) | X | X | X | X | X | X | X | X | X | X | X |
| Integrity of the Blind | | | | | | | X | | | X | |
| Program Satisfaction | | | | | | X | | | X | | |
| OUTCOMES | | | | | | | | | | | |
| Smoking Rate (TLFB) | | X | X | X | X | X | X | X | X | X | X |
| Carbon Monoxide (CO) Test | X | X | X | X | | X | | | X | | X |
| Quality of Life (SF-12) | | X | X | X | X | X | X | X | X | X | X |

*TQD = Target Quit Day *W= Week

*Note: Target Quit Day visit may occur +3 days from target date; Week 4, 8, 12, 14, 18, 24, and 26 visits may occur +/- 1 week from target date. The Week 52 visit may occur +/- 2 weeks from target date. Window extensions are subject to PI approval.

^a Administered only if HADS score exceeds borderline score for either anxiety or depression.

^b Only completed in 50% of participants enrolled at Penn. Will not be administered if participant has discontinued study medication for 14 or more consecutive days prior to scheduled session.

^c Administered only if participant has smoked a cigarette in the past 24 hours.

Screening/Covariate Measures.

Urine Pregnancy Screen

The urine pregnancy screen will assess for current pregnancy in all women and will be administered at the Intake Session.

Breath Alcohol Concentration/ETOH History

The breath alcohol concentration (BrAC) assessment will be administered at the Intake Session. The breath alcohol monitor assesses expired breath for alcohol content. Any reading >0.000 indicates alcohol consumption within the last 14 hours. The ETOH history form will be administered at the Intake Session visit and will ask subjects about their alcohol consumption over the past seven days.

Blood Pressure

Participants presenting at Intake with a blood pressure reading above 160 mmHg systolic and/or 100 mmHg diastolic will be ineligible for the study. Participants presenting at Intake with an elevated blood pressure reading between 150-160 mmHg systolic and/or 90-100 mmHg diastolic will have a second blood pressure reading taken after a ten minute period in which the participants will be instructed to sit comfortably. If, after the second reading:

- A participant has a blood pressure between 150-160 mmHg systolic and/or between 90-100 mmHg diastolic, the study physician will evaluate his/her situation and the participant may be withdrawn from the study.
- A participant has a blood pressure reading above 160 mmHg systolic and/or 100 mmHg diastolic, s/he will be ineligible for the study.

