The following personal health information will be collected as part of this study:

- Name, address, telephone number
- Date of birth
- Social Security Number (W-9 form)
- Some personal information that may be considered sensitive, such as medical history, psychological history, alcohol use history, etc.
- Results from physical examinations, tests or procedures
- Information on medication adherence from the blood sample at the Week 4 visit
- Medical Record Number

Every possible precaution, as described above, will be taken to ensure that the privacy of subjects' personal health information will be maintained.

5. Tissue Specimens

Blood. One 10ml sample of blood will be drawn at Week 4 to evaluate varenicline adherence in 50% of participants enrolled at Penn.

Urine. A urine sample will be required at the Intake Session for pregnancy screenings. Women who test positive for pregnancy will be deemed ineligible

RISK/BENEFIT ASSESSMENT

1. Potential Study Risks

A detailed description of the study will be given to all subjects, which will include the risks of participation, assurance of full confidentiality, and the knowledge that their freedom to refuse participation or withdraw from the project will not affect the availability of treatment at the University of Pennsylvania. Informed consent procedures will comply with current standards of the IRBs at the University of Pennsylvania and Northwestern University. Subjects can choose, as an alternative, to not enroll in this study. Adverse reactions will be assessed and reported as required by Federal law and the regulations of PENN and NU.

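### When Week 0 falls on a later day than Intake, no pregnancy retest is required before first dispensing and the explicit contraception duty has not yet begun (minor safety point)

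*Combined protocol and SAP*

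**What the plan says.** Four places in the combined protocol and SAP put the pregnancy test at Intake and nowhere else:
- Study Procedures, Intake Session, item 2: "A urine pregnancy test (all female subjects) will be administered".
- Table 2, where only the Week -1 column is marked.
- Screening/Covariate Measures: "The urine pregnancy screen will assess for current pregnancy in all women and will be administered at the Intake Session".
- Tissue Specimens: "A urine sample will be required at the Intake Session for pregnancy screenings".

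Drug is first given out at the Week 0 Pre-Quit session: "Medication is dispensed at this session and will begin following the session". The Intake section lets Week 0 fall on the same day as Intake with physician approval, or up to 60 days later. Only if 60 days elapse does this rule apply: "all intake measures must be re-administered and evaluated by the study physician before Pre-Quit can occur".

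Medical exclusion 1 reads "Women who are pregnant, planning a pregnancy within the next 12 months, or lactating". The Reproductive Risks section states that the drug's safety for a fetus is not known. Both that section and inclusion criterion 6 tie contraception to the time on study medication plus at least a month afterwards (criterion 6 also allows abstinence).

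Other safeguards are advice not to become pregnant while on the study, a request to tell staff of an actual or intended pregnancy, and immediate discontinuation of drug if pregnancy occurs, with counselling and assessments continuing.

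**The concern.** Exclusion 1 is checked once, on a day that may be weeks before the first dose. A woman may conceive between the two sessions, or may have conceived too recently for the Intake test to show it. If she does not know she is pregnant, she passes every check the plan requires and is given drug. Both arms take active varenicline for the first 12 weeks, so she would be exposed whichever arm she was in. What is at stake is fetal exposure to a drug whose safety the protocol calls unknown. No estimate, test or power figure is involved.

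Same-day Intake and Week 0 fall outside this point, because the test is then current. So does testing during the 24 weeks of dosing.

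**Working it through.** The plan states no figure to reproduce. The check has two parts.

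**Does any rule close the gap?** Take a woman who tests negative at Intake, conceives on day 10 and attends Week 0 on day 50.
- Exclusion 1: she now meets it, but nothing scheduled reveals this.
- 60-day rule: not triggered, since 50 < 60.
- Contraception duty: it starts with medication, after day 50.
- Planned-pregnancy exclusion: not met, as the pregnancy was not intended.
- Notification and stop rule: both need a known pregnancy.
- Reproductive Risks also asks for a pregnancy test before the study starts. The Intake test satisfies that and does not imply one at Week 0.

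She is dosed with the plan followed exactly.

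**How many such cases?** Inputs from the documents:
- N = 374.
- Women 45% to 55%, from two earlier Penn cessation trials (Target Population section).
- Gap G = 7 days (Week -1 to Week 0) or 60 days (the ceiling).

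Inputs that are assumptions, not in the documents:
- 10% to 25% of the women are of childbearing potential.
- r = 1% to 5% pregnancies per woman-year.
- A urine test turns positive L = 10 to 21 days after conception.

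Women at risk, W: 374 × 0.45 × 0.10 = 16.8 to 374 × 0.55 × 0.25 = 51.4.

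Conceptions in the gap = W × r × G/365:
- G = 7: 16.8 × 0.01 × 7/365 = 0.003 to 51.4 × 0.05 × 7/365 = 0.049.
- G = 60: 16.8 × 0.01 × 60/365 = 0.028 to 51.4 × 0.05 × 60/365 = 0.423.

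Pregnancies undetected at first dose, including those too early to show at Intake = W × r × (G + L)/365:
- G = 7: 16.8 × 0.01 × 17/365 = 0.008 to 51.4 × 0.05 × 28/365 = 0.197.
- G = 60: 16.8 × 0.01 × 70/365 = 0.032 to 51.4 × 0.05 × 81/365 = 0.571.

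| Every woman waits | Conceived in gap | Poisson chance of none | Undetected at first dose |
|---|---|---|---|
| 7 days | 0.003 to 0.05 | 99.7% to 95% | 0.008 to 0.20 |
| 60 days | 0.03 to 0.42 | 97% to 66% | 0.03 to 0.57 |

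At the top of the last column the chance of no case is exp(-0.571) = 56%.

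**Sensitivity to the assumptions.** Take instead women at 48% to 54%, 5% to 30% of them at risk, and a monthly conception probability m of 0.5% to 5%. The expected count is W × [1 - (1 - m)^(G/30.4)].
- G = 7: 0.01 to 0.71. The middle case (15% at risk, m = 2%) gives W = 26.9 to 30.3 and 0.13 to 0.14 expected, with a 12% to 13% chance of at least one.
- G = 60 for everyone: 0.09 to 5.8. The middle case is 1.1 to 1.2.

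**What would a Week 0 retest catch?** Without it, conceptions in the last G + L days are missed. With it, only those in the last L days are missed. The share removed is G/(G + L):
- G = 7: 7/28 = 25% to 7/17 = 41%.
- G = 60: 60/81 = 74% to 60/70 = 86%.
- Same day: 0%.

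Still missed after a test on the dosing day: 16.8 × 0.01 × 10/365 = 0.005 to 51.4 × 0.05 × 21/365 = 0.148.

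**The case against.** The strongest reply is that the plan is consistent and this is a preference for a shorter validity limit on one test. The 60-day rule covers all Intake measures, the pregnancy test included. The Study Duration section counts participation from the initial eligibility assessment, so the advice not to conceive while on the study, and the request to report, reasonably apply before Week 0. Planned pregnancy is excluded. Breath alcohol, another exclusion, is also checked only at Intake.

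Most of that stands. There is no internal contradiction, and a reader who infers that women are left without any safeguard between the sessions goes beyond the text. The documents support something narrower: those safeguards depend on intention or on a recognised pregnancy, and none detects an unrecognised one. Nor does a 60-day limit suit a result that can change within days.

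The plan does withhold drug at Week 0 for high blood pressure, so rechecking an exclusion before the first dose is not foreign to it. The parallel is loose, because blood pressure is also monitored throughout for drug effects.

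**Conclusion.** The point holds as a minor safety gap, limited to women whose Week 0 is on a later day than Intake. The reading of the schedule and rules is secure. The counts are not, because childbearing share, conception rate, detection lag and the spread of gap lengths are all absent from the documents.

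A reader might take the 0.05 and 0.42 as upper bounds. They are not: other plausible inputs give larger values, and they leave out pregnancies too early to show at Intake. It is equally unsafe to say without condition that no case will occur. That is the likely outcome if gaps are mostly short, and it is less secure if long gaps are common.

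Nor should a reader infer any threat to the trial's conclusions. Power and the primary analysis are unaffected.

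**What to change.** (a) Reword inclusion criterion 6 and the Reproductive Risks section so that contraception or abstinence runs from consent at Intake, through the medication period, to at least one month after it ends. This costs protocol and consent wording only.

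(b) Keep the Intake test for all women. For women of childbearing potential whose Week 0 is not the same day as Intake, require a negative urine test before Week 0 dispensing, and amend Table 2, the Urine Pregnancy Screen text and Tissue Specimens to match. Where possible, do the test before the pharmacy assigns the kit number. Under Study Medication that assignment follows once a subject is enrolled and eligible, so a later positive could be a post-randomisation event. If the kit is already assigned, withhold drug, continue counselling and assessments as Reproductive Risks already provides after a pregnancy, and keep the woman in the intent-to-treat analysis.

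Under the first set of assumptions the cost is about 17 to 51 extra dipsticks, fewer if some sessions are same-day. Table 2 lists Week 0 as in person, and medical history review already identifies the subgroup. Rarely, a participant will receive no drug. Very recent conceptions can still be missed, and the retest adds most when the gap is long.

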At NU, the trial will be primarily implemented at the Robert H. Lurie Comprehensive Cancer Center. [name] is Director of the cancer center and will ensure that this trial is integrated into the cancer center clinics to facilitate recruitment. Cancer Center data indicate that ~6000 new patients/year are seen at the NU cancer center. Preliminary data ascertained for this proposal showed that, among 127 eligible cancer patients screened, 17 were smokers (13%) and 12 (71%) agreed to enroll in a smoking cessation program. Thus, based on ~6000 patients available for screening/year, we expect that ~780 will be smokers and ~546 will be interested in this study. Given the trial requirements and inclusion/exclusion criteria, we estimate that we can enroll ~10% of these patients for this trial (Martinez et al., 2009) or ~55 patients/year at NU (total sample at NU = 187 over 4 years).

Both PENN and NU will supplement recruitment with referrals from physicians and other cancer care providers at various cancer treatment centers within the Philadelphia and Chicago metropolitan areas.

Based on our extended therapy and bupropion trial with cancer patients ([name] et al., 2010a, 2010b), we expect that <20% of participants will withdraw from the trial and ~70% of participants will complete follow-up evaluations, which will exceed rates in varenicline trials (Jorenby et al., 2006). As is advised in smoking cessation trials (Hughes et al., 2003), intent-to-treat will be used for primary analyses, with missing outcome data coded as smokers (even due to death).

3. Key Inclusion Criteria

Eligible subjects will be males and females:

1. 18 years of age or older who self-report smoking at least 5 cigarettes per week, almost every week (menthol and non-menthol) on average, for the last 6 months.
2. Who have been diagnosed with a primary or secondary cancer (all sites) or have experienced a recurrence of a previously diagnosed cancer within the past 5 years. Those diagnosed >5 years ago without remission will also be eligible.
3. With a Karnofsky Score of ≥ 50 or ECOG Performance Status score of ≤ 2 within 6 months of enrollment.
4. Able to use varenicline safely, based on a medical evaluation including medical history and physical examination, and psychiatric evaluation.
5. Residing in the geographic area for at least 12 months.

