We will also frequently assess participant treatment reactions with established varenicline symptom checklists and validated suicidality and depression scales. These assessments will be conducted at each visit before, during, and after the treatment phase. Also, given recent reports indicating the potential risk for adverse cardiovascular effects from varenicline (Singh et al., 2011 and www.fda.gov/Drugs/DrugSafety/ucm259161.htm), blood pressure will be assessed at each in-person visit to monitor cardiovascular reactions to study medication.

We will use an established coding and reporting system for side effects used in our ongoing multi-site varenicline trial (U01 DA020830). In this system, study personnel are trained by physicians and psychologists to administer established side effects measures, including validated scales of depression and suicidality. If a side effect report or a score on an established scale indicates a safety concern, site PIs and physicians/psychologists are immediately notified and will determine a course of action (e.g., continue to monitor, stop medication). Participants are given contact information so that, if an adverse event occurs, they can contact study physicians 24-hours a day. These side effects are also coded and managed by PIs and site physicians/psychologists. All serious adverse events are reported to the IRB, NIH, FDA, and Pfizer in accordance with data safety and monitoring reporting procedures, and they may also be referred to an out-patient department at PENN/NU or to the ER. Lastly, a study-specific Data Safety and Monitoring Board will be convened for this trial to monitor side effects.

Outcome Assessments.

The primary outcome variable is 7-day point prevalence abstinence at Weeks 24 and 52, confirmed with CO (Hughes et al., 2003). All participants will be asked to attend the center at Weeks 24 and 52 and CO will be collected for all participants to avoid potential bias. Other outcomes include: 7-day point-prevalence abstinence (CO-verified) at Week 12 and 26, smoking rate, prolonged abstinence to Weeks 12, 24, 26, and 52 (relapse defined as 7 consecutive days of self-reported smoking, after a 2-week grace period), continuous abstinence at Week 12, 24, 26, and 52 (no smoking between the quit day and the follow-up measure), time to 7-day relapse (no grace period), lapse and recovery events, and QOL.

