Smoking status is assessed using the timeline follow-back method (Brown et al., 1998) as done previously (Lerman et al., 2004; [name] et al., 2010b) and by using breath CO to verify self-report. Participants are considered abstinent if they self-report abstinence (not even a puff of a cigarette) for >7 days prior to the Week 24 and 52 assessment and have a breath CO of <10ppm at the time-point (SRNT, 2002; Hughes et al., 2003). As per convention, participants are assumed to be smoking if they self-report to be smoking at the time-point, cannot be reached to provide data at the time-point, fail to provide a breath sample at the time-point, or provide a breath sample at the time-point that is >10ppm (SRNT, 2002).

Cessation/Smoking Rate: Daily smoking (presence and rate) will be assessed at each visit after Intake Session with the well validated timeline followback method (TLFB). These data can be used to assess

the timing and rates of lapses (smoking episodes not lasting 7 days), recovery events (return to abstinence), and relapse events, as well as to monitor changes in smoking rates (i.e., # cigarettes/day). These data will also be used to compute and assess secondary measures of smoking cessation (e.g., continuous and prolonged abstinence).

Carbon Monoxide (CO) Test: Carbon monoxide will be measured at each in-person visit to confirm smoking status.

Other Smoking Measures (secondary)

As per recommendations (Hughes et al., 2003), we will also assess: prolonged abstinence to Weeks 12, 24, and 52 (relapse is 7 consecutive days of self-reported smoking, after a 2-week grace period), continuous abstinence at Weeks 12, 24, and 52 (no smoking between the quit day and follow-up), time to 7-day relapse (no grace period), smoking rate, and lapse (smoking episodes < 7 days) and recovery (return to 24-hour abstinence) events.

Quality of Life (QOL)

The Short-Form Health Survey (SF-12) will assess QOL (Ware et al., 1996). This scale yields physical and mental subscales, has been used to assess cancer patient QOL (McCorkle et al., 2009), has demonstrated validity and reliability (Gandek et al., 1998), and has been used in smoking cessation trials with cancer patients ([name] et al., 2010a). The SF-12 will be administered at all visits following the Intake Session.

2. Statistical Analysis

Power

Power is provided for the primary aims since the exploratory aim is hypothesis generating. All comparisons are 2-sided.

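### Prolonged abstinence and time to relapse fail only on a 7-day smoking run, so some non-daily smokers eligible at entry can count as successes without changing how they smoke

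*Combined protocol and SAP*

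**What the plan says.** Under Key Inclusion Criteria, criterion 1 sets the entry level: participants must "self-report smoking at least 5 cigarettes per week, almost every week", on average over the last 6 months. No criterion requires daily smoking.

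Outcome Assessments lists "prolonged abstinence to Weeks 12, 24, 26, and 52 (relapse defined as 7 consecutive days of self-reported smoking, after a 2-week grace period") among the other outcomes, together with "time to 7-day relapse (no grace period"). Other Smoking Measures (secondary) repeats both definitions without the Week 26 time-point: "relapse is 7 consecutive days of self-reported smoking, after a 2-week grace period". It also covers "lapse (smoking episodes < 7 days) and recovery (return to 24-hour abstinence) events".

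The daily record comes from timeline follow-back: "Daily smoking (presence and rate) will be assessed at each visit after Intake Session". Two other outcomes are stricter. The primary outcome allows no puff in the 7 days before the visit and needs CO confirmation. The plan also has "continuous abstinence at Weeks 12, 24, and 52 (no smoking between the quit day and follow-up").

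Under Data Analysis, Aim 1, prolonged abstinence is analysed with the same logistic model as the primary outcome, and event times with Cox regression. Under Accrual, missing outcome data are coded as smoking.

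**The concern.** The entry rule and the relapse rule do not fit together. Someone who smokes 5 whole cigarettes a week can smoke on at most 5 days of that week. If at least one smoke-free day falls in every 7-day stretch, the relapse event cannot occur, however long the smoking continues. Neither definition contains a criterion for intermittent smoking, a requirement of initial abstinence, or a CO condition. A participant whose smoking is the same at Week 52 as at entry can therefore be a success on prolonged abstinence and be censored in the relapse analysis.

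What is at stake is how the secondary abstinence and relapse results are read. False successes in both arms raise the reported rates and pull the arms together, which weakens these outcomes as support for the primary result.

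**Working it through.** **1. The plan's own figure.** Inputs from Power, Aim 1: 33% versus 47%, N = 374, two-sided alpha 0.05. I assume 1:1 allocation, so 187 per arm. Power = Φ((d − 1.96·se0)/se1), where se0 = √(2·p̄(1−p̄)/187) and se1 = √((p1(1−p1) + p2(1−p2))/187).

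With p̄ = 0.40, se0 = 0.0507 and se1 = 0.0501. Then (0.14 − 0.0993)/0.0501 = 0.81, and power is 79%. The stated 80% is reproduced. The documents give no figure for prolonged abstinence or relapse.

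**2. Regular weekly patterns.** From the quit day (Week 1) to Week 52 is 51 × 7 = 357 days. There are 2^7 − 2 = 126 fixed weekly patterns with 1 to 6 smoking days. Applied day by day, the written rule gives no relapse for any of them at Weeks 12, 24 or 52, with or without the 14-day grace period. Only smoking on all 7 days triggers it.

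**3. Irregular patterns.** Here the number of smoking days per week is fixed, but the days fall at random within each week. The table shows the simulated chance of at least one 7-day run after the grace period.

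| Smoking days per week | By Week 12 | By Week 24 | By Week 52 |
|---|---|---|---|
| 3 | 0% | 0% | 0% |
| 4 | 4–5% | 11% | 24–25% |
| 5 | about 51% | 83% | 99% |
| 6 | about 100% | 100% | 100% |

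At 3 days a run cannot occur, because two adjoining weeks supply at most 3 + 3 = 6 days in a row. If the weekly count also varies, with each day independent, runs form more easily. At an average of 3 days a week the chance is 9%, 20% and 41% by Weeks 12, 24 and 52; at 2 days it is 1%, 2% and 4%. At about 3.6 days a week it is 23%, 48% and 79%.

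**4. Size of the dilution (illustration).** Take 33% and 47% as the true prolonged-abstinence rates. Let a share q of each arm be non-daily smokers who quit at the same rate as everyone else and who, if they keep smoking, are all coded abstinent. The reported rate is p + q(1 − p).

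| q | Standard | Extended | Difference | OR | Power |
|---|---|---|---|---|---|
| 0 | 33.0% | 47.0% | 14.0 points | 1.80 | 79% |
| 5% | 36.4% | 49.6% | 13.3 points | 1.73 | 74% |
| 10% | 39.7% | 52.3% | 12.6 points | 1.67 | 69% |
| 20% | 46.4% | 57.6% | 11.2 points | 1.57 | 58% |

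**5. Missing data.** Accrual expects about 70% to complete follow-up. At q = 10%, suppose 30% of the non-abstainers in each arm are missing and coded as smoking. The rates become 0.33 + 0.10 × 0.67 × 0.7 = 37.7% and 0.47 + 0.10 × 0.53 × 0.7 = 50.7%, a difference of 13.0 points with power about 72%. If instead 30% of each whole arm is missing, all of them non-abstainers, the rates are 0.33 + 0.10 × 0.37 = 36.7% and 0.47 + 0.10 × 0.23 = 49.3%. The inflation is then smaller still, but the difference stays at 12.6 points and power at about 69%.

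**The case against.** The strongest reply is that the problem is narrow. A reader might infer that every non-daily smoker who never changes also never relapses. The irregular-pattern results refute that: at 5 or 6 days a week, one free day that moves around usually lets a 7-day run form. This objection stands and limits the point to regular patterns or fewer smoking days.

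The affected participants may also be few. Under Barriers to Quitting Smoking, the protocol reports that 69–81% of cancer patients who smoke have their first cigarette within 30 minutes of waking, and a mean FTND of 5.3. The entry criterion is a minimum and does not describe the expected sample. This stands too: no share can be taken from the documents.

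The main conclusions are protected. The primary outcome and continuous abstinence would class this person as smoking, and smoking rate is analysed separately. Prolonged abstinence tolerates lapses by design, so disagreement with point prevalence at one visit is not in itself an error. All of this stands.

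The plan also says that it follows published recommendations for these measures, a source not available here. That does not remove the gap: the written rule is what will be programmed, and here it is paired with an entry criterion that admits non-daily smokers.

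**Conclusion.** The concern holds for prolonged abstinence and time to 7-day relapse only. As written, a participant in follow-up whose smoking is unchanged is always coded a success if a smoke-free day recurs regularly. The same is mostly true at about 4 or fewer smoking days a week. The word mostly assumes a fairly steady number of smoking days per week; it weakens near 4 days if the count varies freely.

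The expected consequence is inflated rates in both arms and a diluted contrast. At an assumed 10% share the difference falls from 14.0 to 12.6 points and power from 79% to 69%. That is close to a worst case for that share, because it counts every continuing non-daily smoker as a success and borrows the Week 24 point-prevalence rates.

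A reader might go further and infer a bias in favour of extended treatment, on the idea that active drug after Day 84 makes smoking less frequent without making it stop. The documents give no frequency by arm, so any differential figure would be invented. Nor is there ground to say that the primary result is at risk.

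**What to change.** In Outcome Assessments and in Other Smoking Measures (secondary), define relapse as 7 consecutive days of smoking, or smoking on at least 1 day in each of 2 consecutive weeks. Apply it after the grace period for prolonged abstinence and without it for time to relapse. State how weeks are counted, for example as 7-day blocks from the quit day. Report the present 7-day-only definition as a sensitivity analysis.

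Each of the 126 regular patterns has a smoking day in every week. All would therefore meet the new rule by day 14 + 14 = 28 after the quit day, well before Week 12 (day 77).

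The cost is wording and derivation code, because daily timeline follow-back is already collected. Reported prolonged-abstinence rates will fall slightly, since isolated smoking in two adjoining weeks now counts as relapse, and comparison with trials that used the 7-day rule alone is less direct. The two-week threshold is a judgement and not a figure from the documents, so it should be fixed before unblinding.

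A CO condition at every visit or a longer recovery definition is not needed for this repair. A CO condition could fail someone for a short lapse that the definition permits, and a longer recovery period would depart from the sponsor's established recurrent-event approach.
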